## **Study Location**

Lee County EMS: Lee EMS serves Florida's Lee County, located in southwestern Florida. Lee County's division of EMS operates under a license by the Florida Department of Health. Lee County serves a population estimated by the US Census Bureau as 739,000, 18% of whom are under 18 years of age, and 5% of whom are under 5 years of age. Lee County EMS responds to over 70,000 annual emergencies from 36 EMS stations, and the workforce is comprised of both EMT-paramedics and EMT-Basics. Per usual dispatch protocol and Lee EMS treatment protocol, the pediatric asthma patients experiencing an acute exacerbation (and all respiratory distress patients, for that matter) are treated and transported by EMT-paramedics (i.e., advanced life support (ALS)-level care), the highest level of care in the Lee County EMS system).

Nassau County Fire Rescue Department: Nassau County Fire Rescue Department serves' Florida's Nassau County, the northeastern most county in Florida. Nassau's estimated population under 18 years of age is 16,544 according to the US Census Bureau. Nassau County is comprised solely of EMT-Paramedics (approximately 120), and contains a specific standard operating protocol for pediatric asthma exacerbations.

Sarasota County EMS: Sarasota County EMS serves a Southwest Florida population of over 400,000 people, 14% of whom are under the age of 18. Sarasota EMS employs over 20 ambulance stations to serve that growing population.

Leon County EMS: Leon County EMS serves a population in Florida's panhandle of nearly 300,000, of whom 18% are under the age of 18. Leon County uses 19 ambulance crews to cover 671 square miles and serve an annual call volume of over 30,000.

Walton County Sheriff's Office Fire and Rescue Division: Walton County serves a rural population of over 70,000 persons (20% of whom are under the age of 18 years) in Florida's panhandle with over 100 providers.

Cincinnati Children's Hospital Medical Center: Investigators in Cincinnati have compiled a database of pediatric EMS encounters that include encounters before and after an EMS guideline change they performed in 2016 that added an oral steroid option (prednisolone) for children treated by EMS with an asthma exacerbation.

Baylor College of Medicine, Houston, TX: Investigators in Houston have compiled a dataset of pediatric EMS encounters that include encounters before and after an EMS guideline change performed in 2014 which added an oral steroid option (dexamethasone) for children treated by Houston EMS with an asthma exacerbation who were transported to Texas Children's Hospital.

## **Study Type**

Observational study

This study is an observational study administered by EMS to pediatric asthma patients ages 2 to 18 years. In a pediatric asthma protocol update, all agencies are adding an oral steroid option for all asthma patients except for those who meet certain exclusion criteria, including those who are not stable to take an oral medication. Therefore, we will analyze outcomes from patients who do and do not receive oral steroids from EMS.

**Table 1: Inclusion and Exclusion Criteria**

Inclusion	Exclusion
Ages 2-18 years	Unconscious, hemodynamically unstable, or critically ill -> EMS will proceed with usual critical care (includes IV methylprednisolone as per protocol)
Primary problem: asthma attack	Daily or every other day CS therapy, CS given for this exacerbation at home by legal guardian or in office by medical practitioner
Safe to take an oral medication	Allergy to prednisolone or another CS
Transported by EMS to an ED	Chronic lung disease besides asthma, airway anatomic abnormalities, tracheostomy, immunocompromised, traumatic injury, pregnancy, law enforcement custody, non-English speaking

Data for 12 months before and 12 months after each EMS agency adds an oral CS option to their existing IV CS option will be abstracted from the EMS and ED EMR records. All sites will send de-identified data already linked to ED outcomes from their pre-existing EMS database via RedCap.

## **EMS Identification of Study Patients**

Age 2-18 years

Primary Problem: Asthma  
Exacerbations

Otherwise meets  
inclusion/exclusion criteria

Safe to take oral medication (if  
critically ill, exclude and proceed  
with usual critical care)

## **Treatment & Transport**

EMS usual care per protocol (albuterol  
nebulizer, other medications, etc.)

Give oral steroid (dosing per protocol),  
if protocol change implemented in  
station

Transport mode and destination as  
usual

## **After EMS / ED Encounter**

EMS Enrollment Report for Study Team

EMS and ED Record Abstraction  
Begins (either study team or in-house  
at EMS agency)

## **Study Data Variables**

*PHI is only collected to accomplish EMS to ED record linkage. PHI variables used for linkage are marked below. PHI will be used by local sites to accomplish this linkage. PHI will not be recorded in RedCap nor transmitted to the main site.*

EMS EMR:

- Date of Service (for linkage)
- Name (for linkage)
- EMS Record Identifier (ID) (for linkage)
- Date of Birth (for linkage)
- Home Address (for linkage)
- Age
- Race
- Ethnicity
- Gender
- EMS Scene Location Address
- Any medications given prior to EMS Arrival
- All EMS vital signs and clinical assessments
- All other EMS-administered medications
- All EMS procedures
- EMS Times: Dispatch to scene arrival, scene time, transport time, ED turnaround time
- Dispatch Complaint
- Provider Primary Impression
- Provider Secondary Impression
- Injury (Yes/No)
- ED destination facility name
- Date and Time of arrival at destination facility

ED EMR: (*duplicate demographic information is collected for record linkage purposes*)

- Date of Service (for linkage)
- Name (for linkage)
- Date of Birth (for linkage)
- Home Address (for linkage)
- Age
- Gender
- Race
- Ethnicity
- Insurance (*for economic analysis*)
- Mode of Arrival
- Vital Signs
- All ED administered medications
- All ED procedures
- ED diagnoses
- ED LOS (minutes)
- ED Disposition (Admit - Yes/No/Transfer)
  - If Yes – Floor vs. ICU

- If No – any discharge prescriptions
- If Transfer – to where and why

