## **Human Subjects Protections**

### **Waiver of Informed Consent**

*The data collected from this research study relates to data that would have already been collected on care the children would have already received based on the existing / planned future protocols for care as defined by the EMS agency contributing data for the study. It is not practical for EMS to consent patients during emergency treatment to have their data collected, nor is it practical to ask legally authorized representatives who may or may not be present during the EMS encounter for consent in the midst of emergency treatment for data collection. Further to this, the study is not altering any aspect of EMS treatment, and therefore is retrospectively collecting data AFTER THE ENCOUNTER HAS OCCURRED.*

The use of PHI involves no more than minimal risk to the individuals because multiple steps will be taken (as noted in other sections above and below) to prevent loss of confidentiality. Also, the PHI will not be used for data reporting, since this information will be removed prior to analysis, and the subjects will be coded with a study number. Accessing the patient's records does not otherwise affect their rights or welfare, since personal information will not be released. The data collected from the pediatric population in this research study relates to care that children would have already received based on the existing protocols for care as defined by the EMS agency involved. The investigators/study team will not be directly interacting with the EMS patients. Access to the PHI (incident run number, date of birth, etc.) is necessary, in order to calculate age accurately and link separate records for the same patient encounter in the EMS and ED EMRs. The principal investigator has performed similar previous and ongoing IRB-approved pediatric EMS studies with waiver of consent. Therefore, this study could not be done without obtaining this PHI, because there would be no other way to match link the EMS to ED records or calculate age in an accurate manner.

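### Date of Service is withheld but the ED arrival date is left unmarked, so it is unresolved whether any calendar-time variable reaches a pooled analysis in which steroid receipt is tied to time

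*Combined protocol and SAP*

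**What the plan says.** The design is defined by time. The text under Table 1 calls for "Data for 12 months before and 12 months after each EMS agency adds an oral CS option", and the Treatment & Transport box makes the oral steroid conditional on the protocol change having been implemented in the station.

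The Study Data Variables section sets the rule for identifiers: "PHI variables used for linkage are marked below", and "PHI will not be recorded in RedCap nor transmitted to the main site". Both the EMS and the ED lists contain an entry that begins "Date of Service (for linkage". The EMS list also contains "Date and Time of arrival at destination facility", which carries no linkage mark.

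Other sections repeat the de-identification rule. The text under Table 1 states: "All sites will send de-identified data already linked to ED outcomes from their pre-existing EMS database via RedCap". The Waiver of Informed Consent section states that "the PHI will not be used for data reporting, since this information will be removed prior to analysis". The PHI paragraph under Potential Risks also says that REDCap will hold no patient identifiers.

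Neither list contains a before/after indicator, a protocol-change date, months from the change, calendar month or season. The Statistical Analysis Plan compares steroid with no-steroid groups and plans hierarchical generalized linear mixed models for hospitalization. It names no covariate, and so no period, calendar-time or season term.

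**The concern.** The same encounter date is handled in two ways. As Date of Service it is linkage PHI that stays at the site. As part of the arrival time it is an unmarked study variable. The plan does not say which treatment governs the file that the main site will analyse.

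The gap matters because exposure and time are linked by design. A child can receive an EMS oral steroid only after the change, whereas a child without one may come from either year. Any change in admission practice between the two years then appears as a difference between receipt groups. Whole 12-month windows balance season between the two years, but not between recipients and non-recipients if uptake rises or falls during the later year. An agency random effect, if that is what the hierarchy means, absorbs differences in level between agencies but not change over time within an agency.

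**Working it through.** **Step 1: what reaches the pooled file.**

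- Date of Service is marked for linkage in both lists, so it is not sent.
- Arrival date and time is unmarked. Read by the marking rule alone, it is a study variable and is sent.
- The marks, however, identify PHI used for linkage, while the exclusion covers all PHI. An absent mark therefore does not prove that a field is kept. The EMS scene address is also unmarked, although it may be the same as the home address, which is marked.
- If the arrival date is kept, it gives calendar time and season. It gives before/after only together with each agency's change date, which is not listed. Study Location gives a year of change for Cincinnati and Houston only.

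So the documents do not settle whether a time variable is present.

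**Step 2: how receipt is tied to time.** Take equal numbers of encounters in the two years, uptake u in the later year, none in the earlier year, and uptake unrelated to risk. The share of the no-steroid group that comes from the earlier year is 1/(1 + (1 − u)). With no steroid effect, the spurious crude risk difference is the drift in admission risk times this share. The documents give no uptake or admission rate, so these inputs are assumptions over a range.

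| Uptake u | Share from earlier year | Drift 2 points | Drift 5 points | Drift 10 points |
|---|---|---|---|---|
| 20% | 55.6% | 1.1 | 2.8 | 5.6 |
| 50% | 66.7% | 1.3 | 3.3 | 6.7 |
| 80% | 83.3% | 1.7 | 4.2 | 8.3 |

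**Step 3: the same on the odds-ratio scale.** Assume 1000 children per year, 50% uptake, 30% baseline admission and no true effect.

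- *10% relative fall between years.* Recipients 27%. Non-recipients (1000 × 0.30 + 500 × 0.27)/1500 = 29%. OR = (0.27/0.73)/(0.29/0.71) = 0.3699/0.4085 = 0.91.
- *20% relative fall.* Recipients 24%. Non-recipients (300 + 500 × 0.24)/1500 = 28%. OR = 0.3158/0.3889 = 0.81.
- *Season, no yearly trend.* Admission is 25% in the first half-year and 35% in the second, and uptake rises from 30% to 70%. Recipients (150 × 0.25 + 350 × 0.35)/500 = 32%. Non-recipients (300 + 350 × 0.25 + 150 × 0.35)/1500 = 440/1500 = 29.3%. OR = 0.4706/0.4151 = 1.13.
- *Seasons reversed.* Recipients (150 × 0.35 + 350 × 0.25)/500 = 28%. Non-recipients (300 + 350 × 0.35 + 150 × 0.25)/1500 = 460/1500 = 30.7%. OR = 0.3889/0.4423 = 0.88.

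The plan states no figure of its own on this point, so there is none to reproduce.

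**The case against.** The best defence is that a calendar variable is listed. By the section's own marking rule the arrival date is not linkage PHI, and nothing in the documents expressly classes it as PHI. Sites must also place each encounter before or after the change merely to select records, so a period flag is easy to produce. A site could convert the date to a flag or a month before sending. All of this stands. It rules out saying that the pooled file will have no time variable. It does not show that one will be sent, and a flag alone would not deal with season.

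A reader might also infer that the dates are lost for good once the data are pooled. The documents do not support that. Subjects carry a study number, the data come from databases held by the sites, study staff may do the abstraction and have access to PHI, and no passage says that a key or source record is destroyed.

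A third objection is that the odds ratios measure the omission of time from the model and would be the same with every date in the file. That is correct. Handling of the date fields decides whether adjustment is possible; the model specification decides whether it is done. Both are open in this plan, so the two parts of the fix belong together.

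Finally, all inputs to the illustration are assumed, and the direction of the seasonal bias depends on which half-year has the higher uptake. This also stands, which is why both directions are shown.

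**Conclusion.** The point holds in a limited form. The plan treats two fields that carry essentially the same date in conflicting ways, lists no derived time variable, and names no time term in a comparison where receipt is possible only in the later period. It is unresolved, not established, that the main site will lack calendar time.

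If time is left out of the model, modest drift is enough to move the result: odds ratios of 0.91 to 0.81 for a 10% to 20% relative fall in admissions, and about 0.88 to 1.13 from season with changing uptake, all with no steroid effect. These are crude, single-population values. They rest on equal yearly numbers, 50% uptake, 30% baseline admission, no oral steroid in the earlier year and uptake unrelated to risk. It would be tempting to add that biases of this size match the effect the study seeks, but the documents give no target effect, margin or sample size against which to judge that.

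The matter should be settled before sites strip dates, because it is easiest to fix at that stage.

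**What to change.** 1. In Study Data Variables, reconcile Date of Service with the arrival date and time. State whether the arrival date is sent or is replaced by derived fields.
2. Have each site derive, before removing dates, and send in RedCap: a before/after flag, whole months from the change (−12 to +12), and calendar month. If rollout was by station, as the Treatment & Transport box suggests, date the change by station.
3. In the Statistical Analysis Plan, include calendar time (or months from the change) and season as fixed effects in the hospitalization model.

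The cost is a few derived fields, a sentence or two in the SAP and a few degrees of freedom. Receipt and time are correlated, so the interval for the steroid effect will be somewhat wider. The time terms deal with drift and season only; they do not address any difference in risk between children who are and are not given the steroid within the same period.

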## **Data and Safety Monitoring Plan (DSMP) and Data and Safety Monitoring Board (DSMB)**

Per potential study sponsor (NIH/NHLBI) guidelines and at the specific request of the NHLBI's human subjects officer during administrative review, this study will employ a DSMP and charter a DSMB (see attachment DSMB charter).

### **MONITORING PROCEDURES**

[name] is responsible for oversight and conduct of the study, including that the study is conducted according to the IRB-approved research plan. The IRB has approved this study with waiver of informed consent. Study data will be accessible at all times for the PI and co-investigators to review. The PI and co-investigators will review study conduct including participant accrual, loss to follow-up, and EMS treatment guideline deviations on a monthly basis, and prepare data for reports for quarterly DSMB meetings. The DSMB members will review SAEs individually in real-time once they are discovered, and AEs plus all SAEs in aggregate on a quarterly basis. The PI ensures all protocol deviations, AEs, and SAEs are reported to the IRB, treating EMS agency, and study sponsor (if applicable) according to the UF IRB requirements and those requested by the DSMB as specified in the study DSMB charter. The DSMB members will elect a chair during their first meeting.

### **COLLECTION, SPECIFICATION, AND REPORTING OF SAEs AND AEs**

#### **Specification of Safety Variables**

Safety assessments will consist of monitoring and reporting adverse events (AEs) and serious adverse events (SAEs) that are considered related to EMS administration of oral steroids, all events of death, and any study specific issue of concern.

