#### **Adverse Events**

An AE is any unfavorable and unintended sign, symptom, or disease temporally associated with the EMS administration of oral steroids. Specific AE/SAEs that will be closely monitored for include nausea or vomiting after oral steroid administration, allergic reaction to the steroid (mild, moderate, or severe (anaphylaxis), or suspected aspiration of oral steroid. The study-specific definition of “temporally related” includes within 60 minutes of oral steroid administration.

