## **Serious Adverse Events**

An AE should be classified as an SAE if:

- It results in death (i.e., the AE actually causes or leads to death).
- It is life threatening (i.e., the AE, in the view of the investigator, places the subject at immediate risk of death. It does not include an AE that, had it occurred in a more severe form, might have caused death.).
- It requires or prolongs inpatient hospitalization.
- It results in persistent or significant disability/incapacity (i.e., the AE results in substantial disruption of the subject's ability to conduct normal life functions).
- It is considered a significant medical event by the investigator based on medical judgment (e.g., may jeopardize the subject or may require medical/surgical intervention to prevent one of the outcomes listed above).

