## **Adverse Event Reporting Period**

The reporting period for all study-defined adverse events will begin when the EMS data are abstracted (approximately weekly). AEs are reported to DSMB for their regular quarterly meetings, SAEs must be reported to the DSMB and IRB within 24 hours of becoming aware of the event.

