#### b. Deaths

All deaths that occur during the protocol-specified AE reporting period, regardless of attribution, will be reported to the appropriate parties.

When recording a death, the event or condition that caused or contributed to the fatal outcome will be reported as the single medical concept. If the cause of death is unknown and cannot be ascertained at the time of reporting, report "Unexplained Death".

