#### d. Hospitalizations for Medical or Surgical Procedures

Any AE that results in prolonged hospitalization will be documented and reported as an SAE. If a subject is hospitalized to undergo a medical or surgical procedure as a result of an AE, the event responsible for the procedure, not the procedure itself, will be reported as the SAE.

Hospitalizations for the following reasons do not require reporting: Prolonged hospitalization for diagnostic or elective surgical procedures for preexisting conditions, or hospitalization or prolonged hospitalization for scheduled therapy of the target disease of the study.

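### The safety text promises all deaths and SAEs that prolong a hospital stay, but the listed data end at ED disposition, with no death level and no inpatient outcome

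*Combined protocol and SAP*

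**What the plan says.** Under Specification of Safety Variables, the plan will monitor AEs and SAEs considered "related to EMS administration of oral steroids, all events of death, and any study specific issue of concern". The Deaths subsection repeats the commitment without regard to cause: "All deaths that occur during the protocol-specified AE reporting period, regardless of attribution, will be reported to the appropriate parties".

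On hospital stay, one criterion under Serious Adverse Events reads "It requires or prolongs inpatient hospitalization". The subsection on hospitalizations for procedures adds: "Any AE that results in prolonged hospitalization will be documented and reported as an SAE". Assessment of Adverse Events asks for start and end dates and the patient's outcome for each SAE.

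The data are set out under Study Data Variables. The last ED item is "ED Disposition (Admit - Yes/No/Transfer"). Its follow-on items are "If Yes – Floor vs. ICU" for admitted children, prescriptions for those sent home, and destination and reason for transfers. The only length of stay listed is ED length of stay, in minutes.

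On timing, Adverse Event Reporting Period says: "The reporting period for all study-defined adverse events will begin when the EMS data are abstracted (approximately weekly"). No end is given.

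**The concern.** The safety promise reaches further in time than the data. Deaths of any cause and the later course of an SAE can fall after the child leaves the ED, and nothing on the variable list records what happens then. A site that abstracts exactly what is listed would have no item in which to record an inpatient death or an extended stay.

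What is at stake is the meaning of a negative finding. If the final report says that no deaths and no prolonged stays were recorded, a reader will take it that someone looked. On the listed data, that would not have been shown.

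There is also a small coding problem. A child who dies under EMS care or in the ED fits none of the three disposition levels. The record would have to be entered as not admitted, or left blank and then removed by the complete-observation rule in the Statistical Analysis Plan. The plan does not say which.

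**Working it through.** The plan gives no sample size, event rate or admission rate for this point, so there is no figure to reproduce. The check compares what is promised with what is listed.

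| Event | Where promised | Listed field | Identifiable from the list? |
|---|---|---|---|
| Death under EMS care or in the ED | Specification of Safety Variables; Deaths | None (0 of 3 disposition levels) | Perhaps inferred from vital signs, procedures or ED diagnoses |
| Death after admission or transfer | Same | None | No |
| AE that requires admission | Serious Adverse Events | Admit = Yes | The admission, yes |
| AE that prolongs a stay | Serious Adverse Events; hospitalizations subsection | ED length of stay only | No |
| Outcome and end date of an SAE after the ED | Assessment of Adverse Events | Floor or ICU only | No |

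The next question is whether another route fills the gaps.

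1. *Source records.* The text below Table 1 names EMS and ED records only. The PHI paragraph under Potential Risks first speaks of the ED/hospital record, but then describes abstraction for the EMS and ED encounters. No inpatient variable is named anywhere.
2. *Contact with families.* The waiver section says the team does not interact with patients and argues against contacting them after care. No follow-up is described that would reveal a later death.
3. *Central look-up.* Identifiers stay at the local sites and are not sent to the main site, so the main site cannot trace an inpatient course itself. Local sites would have to be told to do so.
4. *The 60-minute window.* Under Adverse Events, a temporal relation "includes within 60 minutes of oral steroid administration". This limits when an AE begins, not how long its consequences last. Suspected aspiration, one of the named AEs, could begin inside the window and lengthen a stay later. The death rule does not depend on attribution.
5. *Reporting period.* The Deaths subsection covers deaths within the AE reporting period. That period has no stated end, so the documents do not settle whether an inpatient death is in scope.

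None of the five supplies a described way to find a death or a prolonged stay after ED disposition.

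**The case against.** The strongest reply is that Study Data Variables is not the whole safety record. It has no fields for AE onset, severity or attribution, yet the plan requires all of these. There must therefore be a separate investigator-led record, and the plan says that record includes patient outcomes and later follow-up information. One section does mention the hospital record. The DSMB charter, to which Monitoring Procedures defers for reporting requirements, was not available and may describe a route.

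This stands as a limit on the point. A reader might infer that deaths and prolonged stays cannot be captured at all, or that capture is nil. The documents do not support that. They show only that no field or route is specified. Nor do they support treating the serious-event criteria as broadly unobservable: admission shows through the disposition item, AEs that begin within 60 minutes will usually fall in EMS or ED records, and a death in the ED may be visible in other listed items.

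A reader might also infer that the primary outcome should become hospitalization or death. The documents give no basis for that. Table 1 excludes unconscious, unstable or critically ill children, so a death before admission should be very rare and its effect on the analysis negligible. No text says that such a death would be counted as not admitted.

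The objection does not supply the missing instruction. Monitoring Procedures has the DSMB review SAEs once discovered, and the available text does not say how one arising after ED disposition would be discovered.

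**Conclusion.** The point holds as a mismatch between the safety promise and the specified data. For events after ED disposition, an absence of recorded deaths or prolonged stays would not show that none occurred. The gap falls mainly on admitted and transferred children, and on the late consequences of early AEs and later deaths of any cause. Its size in events cannot be derived from the documents; the number of deaths is likely to be very small. The loss is to the safety statement, not to the primary analysis.

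This rests on two assumptions: that the unseen DSMB charter adds no detection route, and that sites abstract what the protocol lists. If the charter does define inpatient follow-up, a cross-reference and the matching fields would be enough.

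**What to change.** - *Study Data Variables:* add a disposition level for death under EMS care or in the ED, so that such a child is neither entered as not admitted nor dropped as incomplete.
- *Same list, for admitted or transferred children whose hospital record the local site can reach:* add vital status at hospital discharge, hospital length of stay and any ICU stay. Record length of stay as a duration, not a date, to keep identifiers out of REDCap.
- *Adverse Event Reporting Period and Deaths:* state when death and SAE reporting ends, at hospital discharge where the record is reachable.
- *Sites that cannot reach inpatient records, including any already compiled dataset (Cincinnati, Houston) that lacks them:* restate Specification of Safety Variables, Serious Adverse Events and Deaths as applying through ED disposition, and make no claim about all deaths.

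The cost is one code for everyone and three fields for the admitted or transferred subset. The PHI and waiver wording may need an update, since it is now argued on EMS-to-ED linkage. Some transferred children will remain unknown and should be reported as such.

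The primary outcome should stay as it is.
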